13.4.5 Analyses of Exploratory Endpoint(s)

All analyses will be provided separately for high- and low-risk groups as noted. The entire infant sample of both risk groups will also be analyzed together where noted. Analyses will be treated as exploratory and hypothesis- generating, so no formal correction for multiple testing will be applied.

Allergist adherence will be analyzed with generalized linear mixed models for high-risk infants in the EEDI1 sample in the same manner as the primary pediatric clinician endpoint with infants as the unit of analysis. The allergist adherence endpoint will be determined as follows:

An allergist is adherent if:

- The allergist recommends introduction following a sIgE test ≤ 0.35 , a skin prick test 0-2mm, a successful supervised feeding or a successful oral graded food challenge.
- The allergist recommends avoidance and continued monitoring after a skin prick test ≥ 8 mm or a failed supervised feeding or oral graded food challenge.

An allergist is non-adherent if:

- The allergist fails to recommend introduction following a sIgE test ≤ 0.35 , a skin prick test 0-2mm, a successful supervised feeding or a successful oral graded food challenge.
- The allergist recommends introduction following a skin prick test 3-7mm without performing a supervised feeding or oral graded food challenge.
- The allergist recommends introduction following a skin prick test of ≥ 8 mm.

Caregiver adherence (yes/no) will be analyzed with generalized linear mixed models in the EEDI2 sample in the same manner as the primary pediatric clinician endpoint with infants as the unit of analysis. Only high risk infants with data on clinician and/or allergist testing will be used in the analysis of caregiver adherence. For the high risk infants in the primary analysis of the exploratory endpoint, partial caregiver adherence (as defined below) will be grouped with non-adherence. The caregiver adherence endpoint will be determined as follows:

For low-risk infants:

- A caregiver is adherent if the caregiver introduces peanut by 12 months of age, regardless of the pediatric clinician's recommendation.
- A caregiver is non-adherent if the caregiver does not introduce peanut by 12 months of age, regardless of the pediatric clinician's recommendation.

For high-risk infants:

- A caregiver is adherent if the pediatric clinician and/or allergist's testing supports the introduction of peanut, and the caregiver introduces peanut products by 7 months of age and continues feedings with at least 6 g of peanut protein over ≥ 3 feedings per week as reported around the infant's 1st birthday ..
- A caregiver is adherent if the pediatric clinician and allergist's testing supports the avoidance of peanut and the caregiver does not introduce peanut products as reported around the infant's 1st birthday.
- A caregiver is *partially adherent* if the pediatric clinician and/or allergist's testing supports the introduction of peanut, and the caregiver introduces peanut products but does not do so by 6 months of age or does not continue feedings with at least 6 gm of peanut protein or over ≥ 3 feedings per week as reported around the infant's 1st birthday.
- A caregiver is non-adherent if the pediatric clinician and/or allergist's testing supports the avoidance of peanut, and the caregiver introduces peanut products as reported around the infant's 1st birthday.

The primary analysis of the exploratory endpoint will be repeated in the EEDI2 sample including pediatric clinician adherence, allergist adherence (high-risk only) and two-way interactions with each other and intervention group, as fixed effects predictors.

The primary analysis of the exploratory endpoint will be repeated in the EEDI2 sample by combining adherence and partial adherence and comparing partial and non-adherence.

Pediatric clinician knowledge of guidelines, attitudes towards implementation, and barriers and facilitators of adherence will be summarized in the pediatric clinician sample with descriptive statistics using pediatric clinicians as the unit of analysis. A proportion adherent summary statistic will be computed for each pediatric clinician and will be related to KABF with generalized linear mixed models as described in the primary endpoint analysis. The final pediatric clinician KABF assessed after primary outcome data collection will be compared between trial arms. Pediatric clinician KABF after primary outcome data collection in the control group will also be compared to the KABF of pediatric clinicians in the intervention arm at initial informed consent. Pediatric clinician KABF in the intervention arm at 6 months after informed consent and after primary outcome data collection will be separately analyzed for change over time. Any pediatric clinician who did not see infants for 4- or 6-month WCC during the 18-month observation period will be excluded from the analyses.

Caregiver survey data on feeding practices, reaction history, and barriers and facilitators to guideline implementation will be summarized in the EEDI2 sample with descriptive statistics using infants as the unit of analysis.

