3.5. Exploratory Endpoint(s)

Allergist Adherence to the PPA Guidelines (Figure 5). Allergist adherence will be assessed once progress notes by the allergist to whom the infant was referred to have been added to the patient EHR and will be determined based on the following four data elements:

1) Skin Prick Test result (0-2 mm, 3-7mm, ≥ 8 mm), 2) peanut sIgE results, 3) results of in-office supervised feeding of peanut products or oral food challenge with peanut products and 4) peanut product introduction/feeding recommendation. These data will be extracted from laboratory test results, if available, and the allergist progress note entered into the patient EHR. If any data elements are missing, however, the allergist adherence will be adjudicated by an expert panel of allergists from the study advisory board.

Figure 5. Allergist Adherence

*We assume that allergists will evaluate any child who is referred to them.

[figure not shown]
Barriers/facilitators for PPA Guideline adherence among pediatric clinicians and caregivers. Barriers and facilitators will be assessed through survey of pediatric clinicians and caregivers.

Caregiver adherence (peanut product introduction and feeding frequency) (Figure 6). Caregiver adherence is conceptualized to be independent of the clinician's adherence. All pathways to adherence (whether full adherence, meaning the clinician and the caregiver adhere, or caregiver adherence despite conflict with clinician recommendation) are described in Figure 6. Caregiver adherence to the PPA Guidelines will be assessed through the caregiver survey completed around the child's first and second birthdays, as well as through the child's EHR records.

[figure not shown]
Caregiver adherence will be determined based on the following five data elements: 1) infant risk category (high- vs. low-risk based on the presence of an egg allergy and/or severe eczema), 2) peanut sIgE testing results, if applicable (negative vs. positive); 3) peanut skin prick test results (if applicable), 4) peanut product introduction (introduced or did not introduce), and 5) peanut product feeding frequency and quantity (feedings per week). These data will be obtained from the caregiver survey (which will assess the timing, amount, frequency, and modes of peanut product consumption by the infant) and from the infant's EHR records (risk category, testing recommended, and testing results).

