6.1. Investigational Agents/Devices/Interventions

6.1.1. Investigational Intervention: Intervention to Reduce Early (Peanut) Allergy in Children (iREACH)

The iREACH intervention consists of **A) an education module** about the PPA Guidelines and the research on which the guidelines were based; **B) an EHR-integrated CDS tool** in the 4- and 6-month WCC templates to support pediatric clinician decision-making around 1) proper triage of infants into peanut allergy risk categories, 2) allergy testing and interpretation and/or allergist referral for high-risk infants, and 3) caregivers counseling on peanut introduction including educational materials for families

and a minor addition to the anticipatory guidance section of the note template to facilitate documentation of PPA Guidelines discussion; and **C) follow-up prompts** in the 9- and 12-month WCC templates guiding pediatric clinicians to ask caregivers about inclusion of peanut products in their child's diet. The components of the intervention are detailed below:

A. Education Module: Text- and video-based educational materials covering the PPA Guidelines, the research on which the guidelines were based, and instructions for using the iREACH CDS tool will be delivered as an online module. Pre-and post-test knowledge surveys will be embedded into the module and permits monitoring of provider compliance with the assigned training. Key study personnel will be available via email, phone, or in-person to answer any questions that arise after completion of the educational module posttests.

B. CDS Tool: A multi-component tool within the EHR that includes the following:

- a. *A Best Practice Advisory (BPA)* will be triggered at 4- and 6-month well child visits to remind pediatric clinicians to evaluate child for peanut product introduction.
- b. *A Smart List* within note template to remind pediatric clinicians to assess the infant for conditions that would classify the infant as high-risk for PA (i.e., egg allergy or severe eczema).
- c. *A Smart Set* (order set) to guide the pediatric clinician in choosing peanut sIgE or allergist referral based upon PA risk status. The pediatric clinician selects orders based upon their assessment of PA risk. This Smart Set includes the option to print out a caregiver educational handout to assist with caregiver counseling on peanut product introduction.

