- d. *A BPA* triggered when the pediatric clinician views peanut sIgE results (for those patients for whom sIgE has been ordered. The BPA will provide the criteria for "positive" results (≥ 0.35 kU/L) and a recommendation to refer to an allergy specialist if results are positive.

Caregiver Handout on How to Introduce Peanut Containing Products: Handout adapted from the NIAID caregiver materials (English and Spanish versions). The handouts were simplified and tested with caregiver groups including low-literacy, underserved families. This handout can be used as part of pediatric clinician counseling and can go home with caregivers as a reminder.

C. Follow-up Prompts at 9- and 12-month WCC: *Smart Texts and Data Elements* that advise the pediatric clinician to ask caregivers and chart whether peanut products have been introduced into their infant's diet. If the caregiver reports that peanut products were introduced, the clinician will be directed to document whether introduction was tolerated. If caregiver reports that peanut products were not introduced, the clinician will be directed to ask the caregiver for reasons why they did not.

Note: For those practices that do not use an Epic-based EHR, Lurie Children's study team will facilitate and work with their informatics teams to implement an iteration of the CDS tool that is compatible with the practice EHR.

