13.2 Endpoints

Primary Endpoints:

- % of infants at *low risk for peanut allergy* whose pediatric clinician adhered to the guidelines for that infant.
- % of infants at *high risk for peanut allergy* whose pediatric clinician adhered to the guidelines for that infant.

Secondary Endpoint:

- % of infants at *low risk for peanut allergy* who developed peanut allergy by age 2.5.
- % of infants at *high risk for peanut allergy* who developed peanut allergy by age 2.5.

Exploratory Endpoint 1:

- % of infants at *high risk for peanut allergy* whose allergist adhered to the guidelines.

Exploratory Endpoint 2: Pediatric clinician and caregiver reported knowledge, attitudes, and barriers and facilitators to PPA Guideline adherence.

Exploratory Endpoint 3: Each of the following endpoints include infants that are fully adherent and those that are adherent despite conflict with the clinician recommendation as defined in Figure 6. The endpoints for high risk infants can only be determined for infants where clinician testing (e.g. IgE and/or skin prick tests) is available in order to determine guideline consistent caregiver behavior.

- % of infants at *low risk for peanut allergy* whose caregiver introduced peanut by 12 months of age.

- % of infants at *high risk for peanut allergy* whose caregiver introduces peanut products by 7 months of age and continues feedings with at least 6 g of peanut protein over ≥ 3 feedings per week as reported around the infant's 1st birthday in accordance with the peanut allergy prevention guidelines.% of infants at *high risk for peanut allergy* whose caregiver introduces peanut products but does not do so by 7 months of age or does not continue feedings with at least 6 g of peanut protein or over ≥ 3 feedings per week as reported around the infant's 1st birthday. 13.3 Measures to Minimize Bias

A minimum of 30 participating clinic sites will be randomized in a 1:1 ratio to the intervention arm (i.e., offering iREACH intervention) or standard care (i.e. without iREACH). Using a computerized random number generator, the randomization will be stratified by practice site size to achieve balanced allocation of participants into the intervention and standard care arms. This process will be performed by the Lurie DCC biostatistician, who is blinded to the intervention delivery and will not be aware of the identity of participating sites.

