13.4 Analysis Plan

13.4.1 Analysis Populations.

Primary EHR data infant (PEDI) sample: All infants meeting inclusion/exclusion criteria for whom EHR data has been obtained at a 4-month or 6-month WCC in order to assess the primary endpoint of pediatric clinician adherence. Data regarding characteristics of the treating pediatric clinician are not required for an infant to be included in this population.

Secondary EHR data infant (SEDI) samples with pediatric clinician characteristics obtained: All infants meeting inclusion/exclusion criteria for whom EHR data has been obtained at a 4-month or 6-month WCC in order to assess the primary endpoint of pediatric clinician adherence and whose pediatric clinician has consented and completed the characteristics questionnaire information. In addition to characteristics obtained through the characteristics questionnaire information, data on completion of pre-study training for pediatric clinicians in the intervention arm will also be captured.

Exploratory EHR data infant (EEDI) samples

- With allergist adherence obtained (EEDI1): All high-risk infants meeting eligibility criteria who are referred to an allergist for testing and for whom data are obtained regarding the testing that was conducted, the outcome of the allergist testing and the recommendation provided by the allergist as to early introduction of peanut-containing food.
- With caregiver adherence obtained (EEDI2): All infants whose caregivers complete the FOABF and Caregiver Account of Clinician Peanut Recommendations, Testing and Introduction surveys at 12 and/or 24 months.

Pediatric clinician sample: All pediatric clinicians within the intervention group meeting consent and eligibility criteria who complete baseline and at least one follow-up knowledge, attitudes, or barriers and facilitators survey. Those clinicians in the control group will complete one follow-up knowledge, attitudes, or barriers and facilitators survey.

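### The exploratory arm comparisons of high-risk caregiver adherence and of allergist adherence keep only infants tested or referred after randomization, steps that iREACH is designed to change, so they may be selected rather than randomized comparisons

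*Combined protocol and SAP*

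**What the plan says.** **Caregiver adherence, high-risk infants.** Section 13.2 limits the endpoint to tested infants and explains why: "The endpoints for high risk infants can only be determined for infants where clinician testing (e.g. IgE and/or skin prick tests) is available"; without a result, the guideline-consistent behavior cannot be determined. Section 13.4.5 repeats the limit for the analysis: "Only high risk infants with data on clinician and/or allergist testing will be used in the analysis of caregiver adherence". The underlying sample, EEDI2 in section 13.4.1, is itself limited by survey completion: "All infants whose caregivers complete the FOABF and Caregiver Account of Clinician Peanut Recommendations, Testing and Introduction surveys at 12 and/or 24 months".

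**Allergist adherence.** EEDI1 in section 13.4.1 is "All high-risk infants meeting eligibility criteria who are referred to an allergist for testing", provided that the testing, its outcome and the allergist's recommendation are recorded.

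**Model.** Section 13.4.5 analyzes both outcomes with the model of section 13.4.2. That model has trial arm and practice volume as fixed effects and a random practice effect, and it yields an odds ratio for iREACH against control. Both analyses are therefore comparisons between arms. Section 13.4.5 labels them exploratory.

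**What iREACH does.** Under section 6.1.1, the order set is there "to guide the pediatric clinician in choosing peanut sIgE or allergist referral based upon PA risk status", and an alert shown with the sIgE result gives "a recommendation to refer to an allergy specialist if results are positive". Every adherent route for high-risk infants in section 13.4.2 requires an sIgE order or a referral. Section 2.1 hypothesizes that adherence is higher with iREACH.

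**The concern.** Entry into both analysis sets is decided after randomization, by clinician actions that the intervention targets. If the primary hypothesis is true for high-risk infants, the tested or referred share is expected to differ between arms, and probably so is the kind of infant and family in it. Randomization balances all high-risk infants in expectation. It does not balance subsets selected by different processes in the two arms.

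At stake is how two exploratory odds ratios are read. A difference could appear although iREACH changed nothing in how caregivers or allergists behave, or a real difference could be masked. A larger sample would not cure this. The plan does not label these contrasts as non-randomized, report tested or referred shares by arm as a check on them, or add an analysis that keeps all high-risk infants. The repeat analysis in section 13.4.5 that adds clinician and allergist adherence as predictors conditions on further post-randomization variables, so it does not remove the problem.

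**Working it through.** **1. The plan's own figure.** Section 13.7 gives 18 points as the detectable difference for primary and exploratory adherence outcomes in about 500 high-risk infants (30 sites, 17 per site, ICC 0.07, mean proportion 0.50, type 1 error 0.05, taken as two-sided).

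- Design effect = 1 + (17 − 1) × 0.07 = 2.12; effective n per arm = 250 / 2.12 = 117.9.
- For 59% vs 41%: pooled SE = √(2 × 0.25 / 117.9) = 0.0651; unpooled SE = √(2 × 0.59 × 0.41 / 117.9) = 0.0641.
- Power = Φ((0.18 − 1.96 × 0.0651) / 0.0641) = 79.3%, or 80.1% with 30 × 17 = 510 infants. The figure reproduces.

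It uses all high-risk infants, however. If half entered the analysis (assumed), the design effect would be 1 + (8.5 − 1) × 0.07 = 1.525, the effective n per arm 125 / 1.525 = 82.0, and power for 18 points about 64%.

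**2. Selection with no true effect on caregivers.** The documents give no testing rates, so everything here is assumed. Let u ~ N(0,1) be an unmeasured family characteristic, P(adherent) = expit(−0.4 + u) in both arms (41.8% overall), and P(tested) = expit(a + g·u), with a set to give the stated tested share. Adherence among the tested is E[P(tested) × P(adherent)] / P(tested).

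| Tested, control vs iREACH | g | Adherence among tested, control vs iREACH | Spurious difference (points) |
|---|---|---|---|
| 20% vs 60% | 1 | 56.2% vs 48.5% | −7.7 |
| 20% vs 60% | 0.5 | 49.7% vs 45.6% | −4.1 |
| 41% vs 59% | 1 | 51.9% vs 48.7% | −3.2 |
| 41% vs 59% | 0.5 | 47.5% vs 45.7% | −1.8 |
| either | 0 | 41.8% vs 41.8% | 0 |
| 20% vs 60% | −0.5 | 34.2% vs 38.0% | +3.8 |
| 20% vs 60% | −1 | 28.2% vs 34.9% | +6.7 |

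The 41% vs 59% rows borrow the plan's 18-point difference as a stand-in for testing rates. Negative g means that less adherent families are tested more often.

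**3. The same point in algebra.** Suppose everyone tested under control would also be tested under iREACH. Write s_C and s_I for the tested shares, A for adherence in those tested either way, and B for adherence in those tested only because of iREACH. With no true effect, the difference is (1 − s_C / s_I) × (B − A). At 41% vs 59%, A = 60% and B = 40% give (1 − 0.41/0.59) × (−0.20) = −6.1 points; swapping A and B gives +6.1. A starker 70% and 30% gives −12.2. The difference is zero if s_C = s_I or A = B.

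**4. Size relative to noise.** With 20% and 60% of 250 per arm tested, 50 and 150 infants are compared. The SE is √(0.562 × 0.438 / 50 + 0.485 × 0.515 / 150) = 0.081 before clustering and survey loss. A bias of −7.7 points would reach p < 0.05 about 16% of the time, and −4.1 points about 8%.

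**5. An all-infant composite.** Scoring every high-risk infant as tested and caregiver-consistent, with untested counted as no, gives at g = 1: 0.20 × 56.2% = 11.2% vs 0.60 × 48.5% = 29.1%, or +17.9 points for iREACH. At 41% vs 59% it gives 21.3% vs 28.7%, about +7.5. Both arise with no caregiver effect at all.

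**The case against.** **Low stakes and a stated reason.** The analyses are exploratory, the objectives in section 2.4 are to determine adherence, and neither section 2.1 nor section 13.6 states an arm hypothesis for these outcomes. Section 13.2 explains why untested infants are left out. All of this stands. It justifies reporting adherence among tested infants, but it does not make the arm contrast a randomized one. In section 13.4.5 the exploratory label serves to waive multiplicity correction, which is a separate matter.

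**Direction.** A reader might infer that the selection makes iREACH look harmful, on the view that the control infants who get tested come from engaged families or have worse disease. The documents do not say who is tested in either arm. The pilot's high-risk data in section 1.4 (5/8 vs 0/1) are too few to show even that testing changes. The sign can reverse, and the bias is zero if iREACH does not change who is included.

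**Internal contradiction.** A reader might also set the restriction against section 3.5: "Caregiver adherence is conceptualized to be independent of the clinician's adherence". That sentence means that a caregiver can be adherent despite a conflicting clinician recommendation. The same section lists sIgE and skin prick results among the inputs, so there is no contradiction.

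**Allergists.** The figures above concern caregivers. Allergists do not receive iREACH, and section 4.1 expects a given allergist to see infants from both arms. The mechanism still applies, since the mix of referred infants can differ by arm, but its size is unknown.

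**Partly handled.** Section 13.4.6 compares baseline characteristics, including the risk components, across infant samples. It does not say that this is done by arm, and it does not cover the tested subset within EEDI2.

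**Conclusion.** The point holds for two exploratory comparisons: high-risk caregiver adherence and allergist adherence. Both condition on testing or referral, which follow randomization and which iREACH is built to change. If it does change who is tested or referred, these odds ratios are not protected by randomization and may be wrong in either direction.

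For caregivers, an illustrative size is about 2 to 8 points. This rests on assumed testing rates and an assumed link between testing and caregiver behavior. It is not a bound: the two-group split with a starker contrast exceeds it, and no dependence gives zero. No size can be given for allergists.

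The main primary and secondary analyses use the PEDI sample and are not touched by this selection. Low-risk caregiver adherence needs no test result and is likewise unaffected, although it remains limited to survey responders.

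**What to change.** Amend section 13.4.5 as follows.

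1. Report the shares of high-risk infants tested and referred, by arm.
2. Present caregiver adherence among tested high-risk infants and allergist adherence in EEDI1 as proportions with cluster-adjusted confidence intervals, labelled as non-randomized.
3. Drop the iREACH-versus-control test and odds ratio in these subsets, including in the repeat analyses that use them.
4. If an arm contrast is still wanted, it may use all surveyed and linked high-risk infants, with the outcome that the infant was evaluated and the caregiver's behavior was consistent with the result. Label it a care-pathway composite, not caregiver adherence: as shown, it can favor iREACH by about 7 to 18 points with no caregiver effect and largely restates the primary endpoint. Tabulate its components, and state that survey response and consent to linkage are also selected after randomization.

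The change needs SAP wording only and uses the same data. The downside is that these two exploratory subset endpoints have no formal arm test.

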Growing Evidence for Earlier Peanut Introduction: In 2008 Du Toit et al. found that early peanut consumption was associated with a 10-fold reduction in PA prevalence among children aged 4-18 years.²⁰ Subsequently, the Learning Early About Peanut (LEAP) study (N=640) tested whether introduction of dietary peanut in high-PA risk infants 4-11 months of age would reduce PA incidence compared to high-risk infants counseled to avoid peanut until age 5 years.²¹ Specifically, the LEAP protocol instructed caregivers in the early introduction arm to feed their infants at least 6g of peanut protein/week. The LEAP study found that early peanut introduction was safe and resulted in an 81% reduction in subsequent development of PA in high-risk children, as well as corresponding modulation of immune responses to peanuts at age 5. Overall, 92% of participants adhered to the intervention, demonstrating its feasibility. Moreover, the follow-up LEAP-ON study found that even after avoiding peanuts for a year, the children in the early introduction arm retained peanut tolerance.²² These findings, in addition to emerging mechanistic evidence for its tolerogenic effects,^{23,24} spurred a dramatic reversal of national guidelines to recommend early peanut introduction. The 2017

NIAID-sponsored Addendum Guidelines for the Prevention of Peanut Allergy in the United States (PPA Guidelines), stratified infants into three

Figure 2. Summary of Addendum Guidelines for the Prevention of Peanut Allergy

| Addendum Guideline | Infant Criteria | Recommendations | Earliest Age of Peanut Introduction |
|--------------------|-------------------------------------|---|--|
| 1 | Severe eczema, egg allergy, or both | Strongly consider evaluation with peanut-specific IgE and/or skin prick test and, if necessary, an oral food challenge. Based on test results, introduce peanut-containing foods. | 4 to 6 months |
| 2 | Mild to moderate eczema | Introduce peanut-containing foods. | Around 6 months |
| 3 | No eczema or any food allergy | Introduce peanut-containing foods. | Age-appropriate and in accordance with family preferences and cultural practices |

classes, each with its own evaluation protocol and recommendation for peanut product introduction (Figure 2). Based on these guidelines, pediatricians should assess PA risk for infants aged 4-6 months and advise accordingly.²⁵ Because the PPA Guidelines recommend peanut introduction for infants in both class 2 and 3

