For low-risk infants, the caregiver is adherent if the caregiver introduces peanut by 12 months of age. For high-risk infants, the caregiver is adherent if the clinician's testing indicates the introduction of peanut and the caregiver introduced peanut products by 7 months of age and continued feeding at least 6g over ≥ 3 feedings per week as reported around the infant's 1st birthday or the clinician's testing indicates avoidance of peanut and the caregiver does not introduce peanut products as reported around the infant's 1st birthday. For high-risk infants, the caregiver is partially adherent if the pediatric clinician and/or allergist's testing supports the introduction of peanut, and the caregiver introduces peanut products but does not do so by 6 months of age or does not continue feedings with at least 6 gm of peanut protein or over ≥ 3 feedings per week as reported around the infant's 1st birthday.

Figure 6. Caregiver Adherence

High Risk

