| Allergy visits | Date of service, peanut product introduction recommendation (NLP based), severe eczema (NLP based), food allergy ICD-10 codes. |
| Peanut testing | Date of test, type of test (peanut sIgE or peanut skin prick test), test result |
| Emergency Department visits | Date of ED visit, food allergy or anaphylaxis ICD-10 codes |

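### The exploratory high-risk caregiver-adherence rule applies a fixed age limit and ignores whether peanut was introduced before or after the supportive test result

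*Combined protocol and SAP*

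**What the plan says.** Section 13.4.5 opens the high-risk rule with a condition on testing: "A caregiver is adherent if the pediatric clinician and/or allergist's testing supports the introduction of peanut". It then adds a condition on age and continued feeding: "the caregiver introduces peanut products by 7 months of age and continues feedings with at least 6 g of peanut protein". Section 3.5 has the same age limit ("the caregiver introduced peanut products by 7 months of age").

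The partial category is worded in two ways. Section 13.2 describes infants "whose caregiver introduces peanut products but does not do so by 7 months of age". In Section 13.4.5, and in the same terms in Section 3.5, it applies when "the caregiver introduces peanut products but does not do so by 6 months of age or does not continue feedings".

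For the main analysis of this endpoint, "partial caregiver adherence (as defined below) will be grouped with non-adherence". A repeat analysis in 13.4.5 pools adherent with partial.

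For infants with severe eczema or egg allergy, Figure 2 in Section 1.1 recommends evaluation first and then: "Based on test results, introduce peanut-containing foods". Table 8.2 lists as extracted data "Date of test, type of test (peanut sIgE or peanut skin prick test), test result", and Section 3.5 says the caregiver survey records when peanut was introduced. Section 3.5 also treats caregiver adherence as conceptually independent of the clinician's adherence.

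**The concern.** The guideline summary makes introduction in high-risk infants depend on a test result, but the scoring rule uses only the child's age. A caregiver who waits for a late evaluation and then follows it can be counted as a failure. One who introduces with no evaluation can be counted as a success once a later test happens to be supportive.

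Two things are at stake. First, the endpoint partly measures how quickly a test was ordered and completed, which depends on clinicians and allergist access. Only intervention-arm clinicians are prompted to order sIgE or refer (Section 6.1.1), and only high-risk infants with test data are analysed (13.4.5). The mix of early and late results can therefore differ by arm, and the arm contrast can move with no difference in caregiver behaviour. Second, the same variable is a predictor in one of the exploratory peanut-allergy models in 13.4.4.

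**Working it through.** **The plan's own figure.** This point disputes no stated figure. The only one covering the endpoint is the detectable difference of 18 percentage points for high-risk adherence outcomes in Section 13.7. With 30 practices, 17 high-risk infants each and an intracluster correlation of 0.07, the design effect is 1 + (17 − 1) × 0.07 = 2.12. Effective size per arm is 250 / 2.12 = 117.9. Around an average of 0.50, the difference detectable with 80% power (two-sided 0.05) is 18.15 points, and power at 18 points is 79.3%. The figure reproduces to within rounding. It serves below only as a yardstick.

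**The rule applied to individual records.** Ages are in months. In the last two columns, yes means counted as adherent.

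| Case | Result | Introduced | Feeding continued | Label | Main analysis | Repeat analysis |
|---|---|---|---|---|---|---|
| a | 5.5, supports | 5.7 | yes | adherent | yes | yes |
| b | 6.3, supports | 6.5 | yes | meets adherent and partial | undefined | yes |
| c | 8.0, supports | 8.2 | yes | partial | no | yes |
| d | 8.0, supports | 5.0 | yes | adherent | yes | yes |
| e | 8.0, avoid | 5.0 | yes | non-adherent | no | no |
| f | 8.0, supports | 5.0 | no | partial | no | yes |
| g | 5.5, supports | 8.2 | yes | partial | no | yes |

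Cases c and d show the inversion. Cases c and g get the same score under both groupings, although one caregiver acted at once on a late result and the other delayed after a timely one. Case b shows the effect of the 6- and 7-month wording: introduction between those ages satisfies both definitions. If the partial bullet took precedence, any caregiver who waited for a test ordered at or after 6 months of age would fall into the partial category.

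**Late results are foreseeable.** Infants may enter at the 6-month visit (4.2), referral without sIgE is one of the adherent clinician routes (13.4.2), and allergy visits are collected to 30 months (8.2.2).

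**Illustrative size.** The documents give no waiting times, so every input here is an assumption. Visits fall at 4.0–4.5 or 6.0–6.5 months, half each. The wait to result is lognormal with log-SD 0.6. Every caregiver introduces within 0–14 days of a supportive result. Introduction age = visit age + wait + lag. The table gives the simulated share of these caregivers who miss the limit.

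| Median wait | Limit at 7.0: both visits | Limit at 7.0: 6-month visit only | Limit at 8th-month birthday: both visits | Limit at 8th-month birthday: 6-month visit only |
|---|---|---|---|---|
| 1 week | 8% | 16% | 0% | 0% |
| 4 weeks | 43% | 81% | 11% | 21% |
| 6 weeks | 54% | 93% | 25% | 44% |
| 8 weeks | 64% | 97% | 38% | 63% |

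**Illustrative arm contrast.** Let *a* be the share who would count as adherent if no result came too late, *w* the share who wait for the test, and *q* the share of evaluations finishing too late. The scored share is *a*(1 − *wq*).

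- Identical behaviour (*a* = 0.80, *w* = 1 in both arms), with *q* = 0.25 in one arm and 0.50 in the other: 0.80 × 0.75 = 60% against 0.80 × 0.50 = 40%. That is a 20-point difference from test timing alone, and its sign follows whichever arm is tested earlier.
- True 59% v 41% (18 points), *w* = 0.90 v 0.50, common *q* = 0.25: 0.59 × (1 − 0.225) = 45.7% against 0.41 × (1 − 0.125) = 35.9%, a scored difference of 9.9 points. With *q* = 0.10 it is 14.7, and with *q* = 0.50 it is 1.7.

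**The case against.** A fixed-age measure can be defended. Section 3.5 separates caregiver adherence from the clinician and counts adherence even against clinician advice. A measure timed from the result is a different quantity, tied to scheduling. This stands as a reason to keep the age-only rule, but not as a reason to ignore order. Section 13.2 links the high-risk endpoint to the guidelines, and the 4-to-6-month entry in Figure 2 is an earliest age, not a deadline.

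The repeat analysis that pools adherent with partial does rescue case c. It also credits cases f and g, and it leaves case d unchanged.

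Figures 6 and 8, which set out the caregiver pathways, are not visible in the text available, and Section 13.2 refers to Figure 6 for the definition. An ordering rule could be there. The bullets in 13.4.5 that say how the endpoint is determined contain none.

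The data are imperfect. Introduction age is recalled around a birthday. Table 8.2 gives test dates only for sIgE and skin prick tests, whereas supervised feeding or an oral challenge may supply the supportive result and may itself be the first exposure. These limits stand and affect the fix.

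A reader might infer that every caregiver who waits is scored non-adherent. That is not so: timely evaluations score as adherent (case a), and the late label is partial, becoming failure only through the main-analysis grouping. Nor is every early introducer adherent (cases e and f).

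**Conclusion.** The point holds in limited form. The visible rule does not use the order of result and introduction. It misplaces caregivers whose evaluation finishes close to or after the age limit, and it credits introduction before evaluation when later testing is supportive and feeding continues. The 6- and 7-month overlap is a plain inconsistency in the text and needs no assumption.

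The size cannot be determined from the documents. The illustrated shares depend on assumed waits and on how the 7-month limit is read, and the arm contrasts on assumed values of *a*, *w* and *q*. They show that the effect could be small, or larger than the 18 points in Section 13.7. They do not show that the arm comparison is biased, and a reader should not take them that way.

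Severity is minor to moderate. Caregiver adherence is exploratory, no primary or secondary conclusion rests on it, and the neighbouring exploratory model in 13.4.4 uses extent of peanut exposure instead.

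**What to change.** In Sections 3.5 and 13.4.5:

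1. Use the extracted test date and the survey-reported introduction timing to classify introduction as before or after the supportive result.
2. Tabulate introduction before evaluation as its own category, by arm.
3. Add a pre-specified analysis that judges timing relative to the result date, and report it beside the age-only rule. The study's allergist panel should set in advance any interval and the handling of supervised feeding or oral challenge. This is a scoring choice and changes no clinical advice.
4. Reconcile the 6-month limit in the partial-adherence text of 3.5 and 13.4.5 with the 7-month limit used elsewhere in those sections and in 13.2, so that the categories do not overlap.
5. Confirm that Figures 6 and 8 agree with the revised text.

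The cost is SAP wording, a derived order variable and one additional analysis, mostly from data already collected. Rules are also needed for imprecise recalled ages and for supportive results that come from a feeding or challenge, whose dates may have to be taken from allergy visit records. All of this should be settled before outcome data are seen by arm.
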